## **15.0 RESEARCH PARTICIPANT REGISTRATION AND RANDOMIZATION PROCEDURES**

### **15.1 Research Participant Registration**

Confirm eligibility as defined in the section entitled Criteria for Patient/Subject Eligibility.

Obtain informed consent, by following procedures defined in section entitled Informed Consent Procedures.

During the registration process registering individuals will be required to complete a protocol specific Eligibility Checklist.

All participants must be registered through the Protocol Participant Registration (PPR) Office at Memorial Sloan Kettering Cancer Center. PPR is available Monday through Friday from 8:30am – 5:30pm at [contact]. Registrations must be submitted via the PPR Electronic Registration System (<http://ppr/>). The completed signature page of the written consent/RA or verbal script/RA, a completed Eligibility Checklist and other relevant documents must be uploaded via the PPR Electronic Registration System.

### **15.2 Randomization**

Patients from the GI medical oncology clinic at MSKCC who meet the inclusion criteria are eligible for enrollment and randomization. We plan to consecutively recruit 78 patients. Patients will be randomized with a 1:1 ratio to the HAI FUDR + systemic chemotherapy, + Panitumumab arm or the HAI FUDR + systemic chemotherapy, - Panitumumab arm. After eligibility is established and immediately after consent is obtained, patients will be registered in the Protocol Participant Registration (PPR) system and randomized using the Clinical Research Database (CRDB), by calling the MSKCC PPR Office at [contact] between the hours of 8:30 am and 5:30 pm, Monday – Friday. Two stratification variables will be used: prior chemotherapy status and clinical risk score (0-2 vs. 3 or more) [See Appendix A, Fong Score]. Patients will be randomized after surgery and immediately prior to study enrollment.

## **16.0 DATA MANAGEMENT ISSUES**

A Research Study Assistant (RSA) will be assigned to the study. The responsibilities of the RSA include project compliance, data collection, abstraction and entry, data reporting, regulatory monitoring, problem resolution and prioritization, and coordinate the activities of the protocol study team.

The data collected for this study will be entered into a secure database. Source documentation will be available to support the computerized patient record.

### **16.1 Quality Assurance**

Weekly registration reports will be generated to monitor patient accruals and completeness of registration data. Routine data quality reports will be generated to assess missing data and inconsistencies. Accrual rates and extent and accuracy of evaluations and follow-up will be

monitored periodically throughout the study period and potential problems will be brought to the attention of the study team for discussion and action.

Random-sample data quality and protocol compliance audits will be conducted by the study team, at a minimum of two times per year, more frequently if indicated.

## **16.2 Data and Safety Monitoring**

The Data and Safety Monitoring (DSM) Plans at Memorial Sloan-Kettering Cancer Center were approved by the National Cancer Institute in September 2001. The plans address the new policies set forth by the NCI in the document entitled —Policy of the National Cancer Institute for Data and Safety Monitoring of Clinical Trials|| which can be found at: <http://cancertrials.nci.nih.gov/researchers/dsm/index.html>. The DSM Plans at MSKCC were established and are monitored by the Office of Clinical Research. The MSKCC Data and Safety Monitoring Plans can be found on the MSKCC Intranet at: <http://mskweb2.mskcc.org/irb/indexx.htm>. There are several different mechanisms by which clinical trials are monitored for data, safety and quality. There are institutional processes in place for quality assurance (e. g. protocol monitoring, compliance and data verification audits, therapeutic response, and staff education on clinical research QA) and departmental procedures for quality control, plus there are two institutional committees that are responsible for monitoring the activities of our clinical trials programs. The committees: *Data and Safety Monitoring Committee (DSMC)* for Phase I and II clinical trials, and the *Data and Safety Monitoring Board (DSMB)* for Phase III clinical trials, report to the Center's Research Council and Institution Review Board.

During the protocol development and review process, each protocol will be assessed for its level of risk and degree of monitoring required. Every type of protocol (e.g. NIH sponsored, in-house sponsored, industrial sponsored, NCI cooperative group, etc.) will be addressed and the monitoring procedures will be established at the time of protocol activation.

## **17.0 PROTECTION OF HUMAN SUBJECTS**

### **17.1 Privacy**

MSKCC's Privacy Office may allow the use and disclosure of protected health information pursuant to a completed and signed Research Authorization form. The use and disclosure of protected health information will be limited to the individuals described in the Research Authorization form. A Research Authorization form must be completed by the Principal Investigator and approved by the IRB and Privacy Board.

#### **17.1.1 Study Costs**

The cost of the study drug, Panitumumab, will be supplied by Amgen. All other costs will be billed to the patient.

### **17.2 Serious Adverse Event (SAE) Reporting**

An adverse event is considered serious if it results in ANY of the following outcomes:

- Death
- A life-threatening adverse event
- An adverse event that results in inpatient hospitalization or prolongation of existing hospitalization
- A persistent or significant incapacity or substantial disruption of the ability to conduct normal life functions
- A congenital anomaly/birth defect
- Important Medical Events (IME) that may not result in death, be life threatening, or require hospitalization may be considered serious when, based upon medical judgment, they may jeopardize the patient or subject and may require medical or surgical intervention to prevent one of the outcomes listed in this definition

Note: Hospital admission for a planned procedure/disease treatment is not considered an SAE.

SAE reporting is required as soon as the participant signs consent. SAE reporting is required for 30-days after the participant's last investigational treatment or intervention. Any events that occur after the 30-day period and that are at least possibly related to protocol treatment must be reported.

If an SAE requires submission to the IRB office per IRB SOP RR-408 Reporting of Serious Adverse Events, the SAE report must be sent to the IRB within 5 calendar days of the event. The IRB requires a Clinical Research Database (CRDB) SAE report be submitted electronically to the SAE Office as follows:

Reports that include a Grade 5 SAE should be sent to [[contact]](mailto:[contact]). All other reports should be sent to [[contact]](mailto:[contact]).

The report should contain the following information:

Fields populated from CRDB:

- Subject's initials
- Medical record number
- Disease/histology (if applicable)
- Protocol number and title

Data needing to be entered:

- The date the adverse event occurred
- The adverse event
- The grade of the event
- Relationship of the adverse event to the treatment (drug, device, or intervention)
- If the AE was expected
- The severity of the AE
- The intervention
- Detailed text that includes the following

- A explanation of how the AE was handled
- A description of the subject's condition
- Indication if the subject remains on the study
- If an amendment will need to be made to the protocol and/or consent form
- If the SAE is an Unanticipated Problem

The PI's signature and the date it was signed are required on the completed report.

For IND/IDE protocols:

The CRDB SAE report should be completed as per above instructions. If appropriate, the report will be forwarded to the FDA by the SAE staff through the IND Office.

### **17.2.1 Reporting of Serious Treatment Emergent Adverse Events to Amgen**

Investigators are required to report to Amgen Drug Safety ANY serious treatment emergent adverse event (STEAE) as soon as possible.

A STEAE is any sign, symptom or medical condition that emerges during Panitumumab treatment or during a post-treatment follow-up period that (1) was not present at the start of Panitumumab treatment and is not a chronic condition that is part of the patient's medical history OR (2) was present at the start of Panitumumab treatment or as part of the patient's medical history but worsened in severity and/or frequency during therapy, AND that meets any of the following regulatory serious criteria:

- Is fatal
- Is life threatening (places the subject at immediate risk of death)
- Requires in-patient hospitalization or prolongation of existing hospitalization
- Results in persistent or significant disability/incapacity
- Is a congenital anomaly/birth defect
- Other significant medical hazard

A hospitalization meeting the regulatory definition for —seriousll is any inpatient hospital admission that includes a minimum of an overnight stay in a health care facility. Any adverse event that does not meet one of the definitions of serious (e.g., emergency room visit, outpatient surgery, or requires urgent investigation) may be considered by the investigator to meet the —other significant medical hazardll criterion for classification as a serious adverse event. Examples include allergic bronchospasm, convulsions, and blood dyscrasias.

Hospitalization for the performing of protocol-required procedures or administration of study treatment is not classified as an SAE.

Serious adverse events will be collected and recorded at least throughout the study period, beginning with the signing of the informed consent through 30 days after the end of the treatment phase or through the safety follow-up visit, whichever is longer.

The investigator should notify the Sponsor of all serious adverse events occurring at the site(s) in accordance with FDA Regulations. The Sponsor will medically review all SAEs. The Sponsor will ensure the notification of the appropriate Ethics Committees/Institutional Review Boards, of all serious adverse events occurring at the site(s) in accordance with FDA regulations.

The study sponsor is responsible for providing all suspected serious adverse drug reactions (SADRs) related or possibly related to panitumumab to Amgen within 1 month of the event. It is possible that Amgen may request follow-up information from the sponsor.

All suspected unexpected serious adverse reactions (SUSARs) related or possibly related to panitumumab and their follow-up reports must be reported to Amgen within 1 working day of

submission to the FDA, IRB or IEC. A copy of any safety report submitted to the FDA, IRB or IEC should be faxed to Amgen, within 24 hours of such submission. All reporting to the FDA must go through MSKCC's IND Office. The sponsor is responsible to ensure that the latest investigator's brochure is used as the source document for determining the expectedness of an SAE.

A copy of any safety report submitted to the FDA, or any other regulatory agency, IRB or IEC, should be faxed with the Amgen Adverse Event fax coversheet to Amgen, within 24 hours of such submission, at:

Amgen Global Safety  
[contact]

REPORTING	FREQUENCY
SADRs	Within 1 month of the event
SUSARs	Within 1 business day of FDA submission

Investigators should not wait to receive additional information to fully document the event before notifying the sponsor of the SAE. Any SAE, if brought to the attention of the investigator at any time after cessation of study drug, and considered by the investigator to be possibly related to study drug, should be reported.

### **17.2.2 Reporting Procedures for All Adverse Events to Amgen**

All AEs occurring after informed consent signing observed by the investigator or reported by the subject (whether or not attributed to investigational product) will be reported. The investigator is responsible for ensuring that all adverse events observed by the investigator or reported by subjects are properly captured in the subjects' medical records.

An adverse event is defined in the International Conference on Harmonization (ICH) Guideline for Good Clinical Practice as —any untoward medical occurrence in a patient or clinical investigation subject administered a pharmaceutical product and that does not necessarily have a causal relationship with this treatment. (ICH E6:1.2). The ongoing review of safety data will include review of clinical AEs and SAEs including skin-related toxicity assessment and laboratory studies. The CTCAE version 4.0 will be used to grade all AEs, except Panitumumab related toxicity which will be graded by modified CTCAE version 3.0 Dermatology Skin Assessment (Appendix B). The investigator is responsible for reviewing laboratory test results and determining whether an abnormal value in an individual study subject represents a change from values before the study. In general, abnormal laboratory or clinical findings without clinical significance (Grades 1 and 2 or based on the investigator's judgment) should not be recorded as adverse events; however, laboratory value changes requiring therapy or adjustment in prior therapy are considered adverse events. All Grade 3 and Grade 4 or clinically significant toxicities will be recorded.

The following adverse event attributes must be assigned by the investigator:

- Adverse event diagnosis or syndrome(s) (if known, signs or symptoms if not known)
- Event description (with detail appropriate to the event)
- Dates of onset and resolution
- Severity
- Assessment of relatedness to study treatment
- Action taken.

Amgen may request follow-up information.

Medically significant adverse events considered related to the investigational product by the investigator or the sponsor will be followed until resolved or considered stable.

It will be left to the investigator's clinical judgment to determine whether an adverse event is related and of sufficient severity to require the subject's removal from treatment or from the study. A subject may also voluntarily withdraw from treatment due to what he or she perceives as an intolerable adverse event. If either of these situations arises, the subject should be strongly encouraged to undergo an end-of-study assessment and be under medical supervision until symptoms cease or the condition becomes stable.

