## **11.0 TOXICITIES/SIDE EFFECTS**

All toxicities will be rated as per the NCI Common Toxicity Criteria, with the exception of skin or nail related toxicities, which will be graded using CTC version 3.0 with modifications (see appendix B). Hepatic enzyme toxicities will also be captured according to the schema on page 30 as well (see FUDR Dose Modifications and Table I).

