### **11.2 Toxicity Related to Panitumumab**

Toxicities will be recorded as adverse events on the Adverse Event case report form and must be graded using The National Cancer Institute's Common Toxicity Criteria (CTC) version 4.0.

Dermatologic Toxicity: Dermatologic toxicities occurred in 89% of patients and were severe (NCI-CTC grade 3 and higher) in 12% of patients receiving Panitumumab monotherapy. The clinical symptoms include, but are not limited to, dermatitis acneiform, pruritus, erythema, rash, skin exfoliation, paronychia, dry skin, and skin fissures. In some cases, it may cause infected sores requiring medical and/or surgical treatment, or cause severe skin infections that could be fatal. Subsequent to the development of severe dermatologic toxicities, infectious complications, including sepsis, septic death, and abscesses requiring incisions and drainage were reported.

Infusion Reactions: Severe infusion reactions included anaphylactic reactions, bronchospasm, and hypotension, which occurred in approximately 1% of patients.

Pulmonary fibrosis: In patients enrolled in clinical studies of Panitumumab, pulmonary fibrosis occurred in less than 1% (2/1467). Patients with a history of interstitial pneumonitis, pulmonary fibrosis, evidence of interstitial pneumonitis, or pulmonary fibrosis were excluded from clinical studies. Therefore, the probability of risk in a general population is uncertain.

**Electrolyte Depletion/Monitoring:** In patients enrolled in a clinical trial, 2% experienced hypomagnesemia (NCI-CTC grade 3 or 4), which required oral or IV electrolyte repletion. Hypomagnesemia occurred 6 weeks or longer after the initiation of Panitumumab. In some patients, both hypomagnesemia and hypocalcemia occurred.

**Photosensitivity:** Exposure to sunlight can worsen dermatologic toxicity. It is recommended that patients wear sunscreen and hats and limit sun exposure while receiving Panitumumab.

**Dermatologic, Mucosal, and Ocular Toxicity:** Ocular toxicities occurred in 15% of patients and included, but were not limited to: conjunctivitis (4%), ocular hyperemia (3%), increased lacrimation (2%), and eye/eyelid irritation (1%). Stomatitis (7%) and oral mucositis (6%) were reported. One patient experienced an NCI-CTC grade 3 event of mucosal inflammation. The incidence of paronychia was 25% and was severe in 2% of patients. Nail disorders were observed in 9% of patients.

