##### Non-skin- or nail-related toxicities:

Any grade 3 or 4 toxicity with the following exceptions:

- Panitumumab will only be withheld for symptomatic hypomagnesemia and/or hypocalcemia that persists despite aggressive magnesium and/or calcium replacement
- Panitumumab will only be withheld for grade 3 or 4 nausea, diarrhea, or vomiting that persists despite maximum supportive care
- Panitumumab will only be withheld for grade  $\geq 3$  anemia or grade 4 thrombocytopenia that cannot be managed by transfusion(s) or cytokine therapy

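### Sections 11.0, 11.2 and 17.2.2 set conflicting grading scales for skin and nail toxicity, so the same event can be graded differently in the two arms

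*Combined protocol and SAP*

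**What the plan says.** Three places in the protocol say how toxicity is graded.

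- Section 11.0, which opens the toxicity chapter: "All toxicities will be rated as per the NCI Common Toxicity Criteria", with no version number, "with the exception of skin or nail related toxicities, which will be graded using CTC version 3.0 with modifications". The exception is defined by organ. It applies whatever the cause and in either arm, and it points to Appendix B.
- Section 11.2, on panitumumab toxicity: events "must be graded using The National Cancer Institute's Common Toxicity Criteria (CTC) version 4.0". No skin or nail exception is stated, and the section goes straight on to dermatologic toxicity.
- Section 17.2.2, on adverse event reporting: version 4.0 applies to every adverse event, "except Panitumumab related toxicity which will be graded by modified CTCAE version 3.0". The instrument named there is the skin assessment in Appendix B. The exception is defined by attribution to panitumumab.

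Several other provisions use grades. Section 17.2.2 requires grade 3 and 4 or clinically significant toxicities to be recorded, and generally leaves out findings of no clinical significance, such as grades 1 and 2. Section 11.4.5 allows panitumumab to restart after a skin or nail event at grade 2 or lower, as one of several alternatives. The non-skin withholding rule in section 11.4.4 reads "Any grade 3 or 4 toxicity with the following exceptions". Sections 11.4.4 and 11.4.5 do not say which scale the grade comes from. Toxicity is the first secondary objective (section 2.0) and is to be summarised descriptively in each arm (section 14.0).

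**The concern.** A per-arm toxicity summary can be read across arms only if the same event gets the same grade in each arm. That requires the scale to depend on what happened to the patient and not on which drug is thought to have caused it. Section 17.2.2 makes it depend on the second. Arm B receives no panitumumab, so none of its events can be attributed to panitumumab, and a skin event there falls under version 4.0. A similar event in Arm A falls under modified version 3.0 if the investigator attributes it to panitumumab, and under version 4.0 if it is attributed to chemotherapy. Section 11.0 would put all three on the same scale. Section 11.2 would move the panitumumab-attributed event back to version 4.0.

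Skin toxicity is where this matters most, since section 3.2.2 names it as the most frequent panitumumab toxicity and it is where the arms are most likely to differ. The protocol also foresees skin events without panitumumab: section 5.3 lists dermatitis for fluorouracil, and section 11.4.1 has a row for hand/foot skin reactions. What is at stake is a common scale for a secondary objective, and certainty about which grade feeds the recording and re-treatment rules.

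**Working it through.** No formula applies, because the point rests on no sample size, error rate or event count. The check sets the rules side by side for each class of event. For section 17.2.2 two readings are shown: the literal one (every panitumumab-related toxicity goes to Appendix B) and a narrow one (only panitumumab-related skin or nail toxicity does).

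| Event class | 11.0 | 11.2 | 17.2.2, literal | 17.2.2, narrow |
|---|---|---|---|---|
| Skin/nail, attributed to panitumumab (Arm A only) | modified 3.0 | 4.0 | modified 3.0 | modified 3.0 |
| Skin/nail, not attributed to panitumumab (some of Arm A, all of Arm B) | modified 3.0 | not addressed | 4.0 | 4.0 |
| Other, attributed to panitumumab (Arm A only) | CTC, no version | 4.0 | skin scale | 4.0 |
| Other, not attributed to panitumumab | CTC, no version | not addressed | 4.0 | 4.0 |

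Reading across the rows:

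1. Panitumumab-related skin or nail events: section 11.2 conflicts with 11.0 and with 17.2.2 on either reading.
2. Other skin or nail events: 11.0 conflicts with 17.2.2 on either reading.
3. Panitumumab-related events outside skin and nail: on the literal reading, 17.2.2 conflicts with 11.2 and departs from 11.0. On the narrow reading no conflict remains, only the missing version in 11.0.
4. All other events: there is no conflict, only the missing version.

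Reading down the skin and nail rows, 11.0 alone gives both arms one scale. Section 17.2.2 gives modified 3.0 in the first row and 4.0 in the second on either reading, which is the difference between arms.

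Where the grade is then used:

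- Recording (17.2.2): affected. Whether a skin event counts as grade 3 can depend on the scale, although clinically significant toxicities are recorded whatever their grade.
- Skin/nail re-treatment (11.4.5): affected through the grade 2 alternative. The other alternatives (tolerability, or no further need for systemic steroids or for IV antibiotics or antifungals) do not use grade.
- Skin/nail withholding (11.4.4): not affected. The criteria are an infection needing IV treatment, or a serious adverse event.
- Non-skin withholding (11.4.4): grade-based, but touched only by the literal reading of 17.2.2 and by the missing version in 11.0.
- Hand/foot skin reaction (11.4.1): read off a grade with no scale named. Whether Appendix B covers this event cannot be seen.

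**The case against.** The strongest reply is that this is loose drafting with one sensible reading. Section 17.2.2 names a skin instrument, Appendix B is titled as a skin and nail assessment, and section 11.0 confines the exception to skin and nail events and cites the same appendix. Section 11.2 sits under 11.0 and could be read as subject to its exception. On that view non-skin events go to the common criteria, skin and nail events go to Appendix B, and no more than a tidy-up is needed. Section 14.0 also plans only descriptive summaries within each arm, with no test of toxicity between arms.

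Much of this stands, and it rules out several stronger conclusions that a reader might draw.

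- That diarrhoea or hypomagnesaemia must be graded on a skin scale. This is the literal wording of 17.2.2, but given the instrument named it is probably a slip.
- That the conflict changes when panitumumab is withheld for skin toxicity. It does not, because those criteria carry no grade. The grade-based rule covers non-skin events only, and within it hypomagnesaemia and diarrhoea have their own conditions.
- That nearly every Arm A patient would be regraded. The protocol gives dermatologic toxicity of 91% (section 3.2.2) and 89% (section 11.2) on monotherapy, or about 35 of 39 if carried over (0.89 × 39 = 34.7; 0.91 × 39 = 35.5). These are rates of any grade. The severe rate is 12%, or about 5 of 39 (0.12 × 39 = 4.7). Neither figure shows that any grade would change. Likewise 1/39 = 2.6 points is only the step made by one patient in a per-arm rate.
- That grade 3 and 4 rates cannot be compared at all. On the narrow reading only skin and nail grading is in doubt.

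What the reply does not remove is that 11.2 states no exception, and that 17.2.2 defines its exception by attribution. Confining 17.2.2 to skin events leaves both conflicts in place.

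**Conclusion.** The concern holds for skin and nail toxicity. The three sections cannot all be followed. Under 17.2.2 as worded, skin events in the two arms can be graded on different scales, and within Arm A the scale depends on the investigator's view of cause. The recording rule in 17.2.2 and the grade-based alternative for skin and nail re-treatment in 11.4.5 inherit the ambiguity. Outside skin and nail events, what remains on the sensible reading is the missing version number in section 11.0.

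The effect on reported grades cannot be sized. The documents do not compare the two scales, and the content of Appendix B is not in the text available. The conclusion rests only on the wording of the three sections and on panitumumab being given in Arm A alone. The primary endpoint, 15-month RFS, and its decision rule are untouched. It should still be corrected, because the rule as written is inconsistent, it bears on a stated secondary objective, and an event not recorded because of the scale used may not be recoverable at analysis.

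**What to change.** Reconcile sections 11.0, 11.2 and 17.2.2 to one scale and version for each class of event. Define the classes by type of event and not by attribution, and apply them identically in both arms. One way, which follows the structure of section 11.0, is version 4.0 for all events, with the Appendix B scale for skin and nail events of any cause. In detail:

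- Section 11.0: state the version for events outside the exception.
- Section 11.2: add the skin and nail exception, or refer back to 11.0.
- Section 17.2.2: replace the exception for panitumumab-related toxicity with one for skin and nail events.
- Sections 11.4.4 and 11.4.5, and the hand/foot row in 11.4.1: add a reference to the agreed scale. The thresholds and actions in those rules are not at issue here.

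The cost is wording in three sections plus the cross-references, with no new data collection. If events have already been graded, the scale used for each should be documented, and skin and nail events not graded on the agreed scale should be identified before the toxicity tables are produced.
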